The study proposed here will test the hypothesis that rates of stillbirth will be reduced by introduction of a package of care consisting of strategies for increasing pregnant women's awareness of the need for prompt reporting of decreased fetal movements, followed by a management plan for identification of placental insufficiency with timely delivery in confirmed cases. The odds of stillbirth fell by 30% after the introduction of a similar package of care in Norway but the efficacy of this intervention (and possible adverse effects and implications for service delivery) have not been tested in a randomized trial.

We plan a stepped wedge cluster design trial, in which participating hospitals in the UK will be randomized to the timing of introduction of the care package. Outcomes (including the primary outcome of stillbirth) will be derived from Scotland and Ireland's detailed routinely collected maternity data, allowing us to robustly test our hypothesis. A nested qualitative study will examine the acceptability of the intervention to patients and health care providers and identify process issues (barriers to implementation).

1 INTRODUCTION

1.1 BACKGROUND

Stillbirth (defined in the UK as a baby born dead after 24 weeks of completed pregnancy) remains the major cause of perinatal mortality in resource rich environments, with a recent series of papers in the Lancet on stillbirth issue calling for major action in this area (1). There is no single "cause" of stillbirth, and many stillbirths remain unexplained, but fetal growth restriction, hypertension and low socioeconomic status are amongst the identifiable risk factors (2).

The purpose of this study is to test the efficacy of a package of interventions consisting of strategies for increasing pregnant women's awareness of the need to report early when they perceive a reduction in fetal movements, in combination with a management plan for identification and delivery of the "at risk" fetus in such women. Our primary outcome is stillbirth.

The concept that more can be done to reduce stillbirth in the UK and Ireland is supported by data showing a marked variation in rates between resource rich countries, when similar definitions of stillbirth are used (3). Notably, the UK has the highest rates amongst a group of resource rich countries such as Germany, Spain, New Zealand and Italy, with rates in the UK some 50% greater than those of Germany. Rates of stillbirth in Scotland and Ireland, at 4.9 per 1000 livebirths (Scotland, 2010 and Ireland 2009 (4, 5)) are only marginally better than rates in England and Wales at 5.1 per 1000 livebirths (England and Wales, 2010)(5).

So what can be done to reduce rates of stillbirth further? Scottish ministers see the reduction of avoidable harm for women and babies as a major priority and asked the Scottish Government (SG) Health Department to set up the Stillbirth Working Group in 2011. This group works to implement SG policy within the Scottish Government Refreshed Framework for Maternity Services, and works in partnership with Sands (the Stillbirth and Neonatal Death Society). SG, through the Stillbirth Working Group has provided funding for Sands to improve bereavement services. As a result of this and other initiatives, many Health Boards in Scotland have already invested heavily in applying current best evidence, including addressing social inequalities, encouraging smoking cessation programmes and initiating strategies to prevent and / or manage obesity and to identify and tailor care for those at high risk. The equivalent bodies in England, Wales and Ireland (in Ireland through Perinatal Ireland) are also working on similar strategies. However, many evidence gaps remain.

So what research is needed on prevention of stillbirth? Using a robust priority setting strategy (6) the Lancet Stillbirth's series steering committee identified issues around detection and management of reduced fetal movements amongst the top ten key research questions on prevention and management of stillbirth (3) . In this study, we will test an intervention package aiming to encourage early presentation of women experiencing decreased fetal movement, followed by appropriate investigation and targeted intervention, in order to reduce stillbirth. The intervention package is informed by current understanding of the risk factors / aetiology of stillbirth and will be evaluated in a stepped wedge cluster randomised trial.

Association between decreased fetal movements, placental dysfunction and stillbirth

There is a clear association between maternal perception of decreased strength of fetal movement and late stillbirth. In a recent series of 2000 women, the adjusted OR (95% CI) of late stillbirth in women with decreased fetal movement (compared with controls) was 2.37 (1.29-4.35) (7). Although the mechanisms have not been fully delineated, it is likely that decreased fetal movement and stillbirth are linked by a common pathology, that of placental dysfunction. There is good evidence linking placental dysfunction and decreased fetal movement. Women who have fewer fetal movements on ultrasound immediately prior to caesarean section are more likely to have umbilical cord gas measurements indicative of acidaemia, hypoxaemia, and hypercapnia, compared with controls (8). Applicant [name] has shown that women delivering within one week of an episode of decreased fetal movement show differences in placental structure and function, including greater signs of infarction (compared to those with normal fetal movements) (9). Additionally, in a series of over 2000

women (conducted by applicant [name]), the odds of fetal growth restriction (FGR, defined as being at less than the 10th centile for gestation adjusted birthweight) were greater in women with decreased fetal movement compared with controls, with adjusted OR of 1.6, 95% CI 1.1–2.2 (10). Taken together these data are strong evidence that placental dysfunction is associated with decreased fetal movement, and a causative pathway seems likely.

The evidence linking placental dysfunction and stillbirth is even stronger. Amongst the 291 stillbirths in Scotland in 2010, 137 (47%) had evidence of placental dysfunction (4). Given that the placenta was examined in only 80% of stillbirths, the true prevalence of placental dysfunction is likely to be higher. Over 20% of stillborn babies had FGR. Additionally, the Lancet reports notes that “placental pathologies accounted for one in four deaths across all gestational ages, and were contributory or causal in more than half of cases” (11). *If decreased fetal movement is a “biomarker” of placental dysfunction, and placental dysfunction itself is associated with stillbirth, then better management of women presenting with decreased fetal movement might reduce the risk of stillbirth.* Although prenatal detection of fetal growth restriction is improved by fetal movement counting (12), a systematic review (13), and a large and influential cluster randomised trial (which dominates the systematic review) showed that routine fetal movement counting had no effect on perinatal mortality (14). Thus after reviewing the literature, the National Institute for Clinical Excellence (NICE) recommended that “Routine formal fetal movement counting should not be offered” (15). Importantly, the large cluster randomised trial tested a specific alarm limit for decreased fetal movement, but did not inform management of women who did present with decreased fetal movement. More women in the fetal movement counting arm came in with a live baby who subsequently died compared with the control arm (19 vs 11), suggesting that the strategy failed because of inadequate investigation and management of those presenting with decreased fetal movements.

Efficacy of a package of interventions around decreased fetal movement

Supportive data on the package of interventions we propose comes from a large study observational cohort “clinical quality improvement study” in Norway led by applicant [name] (16). In this study, a significant fall in rates of stillbirth (from 3.0/1000 to 2.0/1000 [OR 0.67 95% CI 0.48–0.93]) was observed after introduction an intervention package consisting of written information for women about detection of decreased fetal movements combined with consensus guidelines for health professionals about their management (16). Although this study was not randomised, and therefore constitutes only level II-3 evidence, it has led to new recommendations from the Royal College of Obstetricians and Gynaecologists that “women should be advised to be aware of their baby’s individual pattern of movements and that if they are concerned about a reduction in or cessation of fetal movementsthey should contact their maternity unit” (17). Importantly, in the Norwegian study, there was no increase in the proportion of women who presented with decreased fetal movement when rates were compared before and after the intervention (16). However, women with decreased fetal movements presented significantly earlier to hospital with decreased fetal movements than they had hitherto. Taken together, these data suggest that a package of interventions encouraging women with decreased fetal movements to present early to hospital, combined with a structured approach to the management of women with decreased fetal movement might reduce rates of stillbirth without contributing to a large increase in admissions antenatally. In the study described in this application we plan to formally test (using gold standard methodologies) whether a similar package of interventions really does decrease stillbirth, whether it does any harm (e.g. by increasing rates of caesarean section or induction of labour) and how it can be implemented to best effect in a very different setting.

Optimal strategy for quantification of decreased fetal movement.

A systematic review has failed to define an optimal strategy for the quantification of decreased fetal movement (13). We are currently in the process of performing an up to date systematic review, although a preliminary literature search (see above) has revealed no new information. There is no uniform threshold of fetal movements above which perinatal morbidity increases (18), so that guidelines from the RCOG (17), informed by the Norwegian study (16) suggest that it is maternal perception of decreased fetal movement which is important. We will use a similar approach, encouraging women to present early if they have this perception. A leaflet will be developed emphasizing the importance of decreased fetal movement as a signal to

seek immediate advice from a midwife / maternity centre. The effects of the leaflet will be amplified by a web based education package developed for midwives and other clinicians to teach them to encourage behaviour change in pregnant women, with re-enforcement at several times during pregnancy. We will also encourage clinicians to take maternal perception of decreased fetal movements seriously, and to follow a structured management plan in further risk stratification to determine which babies should be delivered promptly.

Optimal strategy for investigation and management of women presenting with decreased fetal movement.

As shown in a recent systematic review, there are no proven strategies for the investigation and management of women presenting with decreased fetal movement (19). Cardiotocography (CTG) (either analogue or digital) is routinely used to ascertain fetal wellbeing, and it is the cornerstone of the RCOG guideline around decreased fetal movement (17). However, data from Norway, suggests that ultrasound assessment of fetal size is often the most helpful investigation, performing well on both an absolute basis, and compared with other interventions (20). In a series of over 3000 women with decreased fetal movements, ultrasound (including measurement of liquor volume and growth measurements) was found to be useful in detecting abnormalities in 11.6% of scans. In 71% of women in whom an abnormality was found, ultrasound was the only technique that detected an abnormality. Additionally, 85% of abnormalities detected by ultrasound, were important in informing the clinical management of the woman (20). These data are supported by our own recent smaller UK study, where we found that abnormal CTG and abnormal ultrasound scan were the two investigations most strongly associated with poor outcome in women presenting decreased fetal movements, with identification of abnormal estimated fetal growth centile on scan being the test most highly predictive of poor outcome (21). Perhaps this is not surprising, given the strong association between small for gestational age babies and the central importance of ultrasound in the identification and management of such cases (22). Given these data, it is worrying that a survey of clinicians in Scotland (described in detail below) shows that less than 5% would routinely refer women with decreased fetal movements for ultrasound examination. We believe that current investigation of women presenting with decreased fetal movement is inadequate, hence using best available evidence, we have drafted what we consider to be a robust evaluation protocol for investigation of women with decreased fetal movement (attached in Appendix 4). This guideline will be further modified in consensus workshops informed by ongoing cohort studies with all relevant stakeholders (including representatives from each unit, whom we are beginning to identify) before the commencement of the study.

Potential harms of a package of care around increased awareness and optimised management of decreased fetal movements.

Any clinical intervention which aims to improve outcomes also has the ability to do harm. Thus it is essential that the intervention proposed is rigorously evaluated using the gold standard technique of a randomised trial, rather than being introduced as a service development. There is a small window of opportunity to do this, as the Stillbirth Working Group's enthusiasm to improve current management is such that routine introduction of the package of care is unlikely to be delayed much further than the current scheduled end date of this study. Possible harms of a package of care consisting of a management plan for identification and delivery of the "at risk" fetus, together with strategies for increasing pregnant women's awareness of the need to report early include increased maternal anxiety and increased intervention (including hospital admission, induction of labour and caesarean section) which itself is associated with pregnancy related complications. The available evidence is reassuring on some of these issues. Encouraging women to be aware of fetal movement does not increase maternal anxiety (23), and it has a neutral effect on maternal- infant attachment (24), however further research is required. In the Norwegian service development study, the package of care increased rates of follow up of women, but there was no increase in admissions overall, admissions for induction or admissions for emergency caesarean section (16) – again, whilst reassuring these outcomes require formal evaluation in a randomised and relevant setting.

The final possible harm of the package is around increased health care costs. We will not have sufficient resource to perform a formal economic evaluation in this application, but we would be happy to apply for separate funding for this if considered appropriate.

Literature search

A literature search on “decreased fetal movement” and “detection” generated 12 publications, most of which were not relevant, and none of which were randomised trials evaluating different strategies for detection of decreased fetal movement. We are aware of a systematic review on fetal movement counting for assessment of fetal wellbeing (13), which we will update immediately prior to starting this study.

A second literature search on “decreased fetal movement” and “management” generated 30 publications, including a Cochrane systematic review published in April 2012 (19). No randomised trials were identified as suitable for inclusion in this review. The applicants have looked at the remaining 29 papers from this literature search, and many, including the most relevant one of the “clinical quality improvement” unrandomised observational study in Norway by applicant [name] (16) have informed the design of our interventions and are cited in this application.

Results of pilot studies

Applicants [name] and [name] both have an extensive track record on fetal movement counting - many of these studies have informed the background to this application and are cited in the text. The most relevant is the Norwegian observational cohort study (16). We have conducted two surveys of clinician practice around encouraging maternal fetal movement detection (including seeking advice of perceived movement decreases) and management of women presenting with decreased fetal movements. The first survey conducted in England and Wales in 2008 by [name], prior to the introduction of the RCOG guideline (17) had responses from 223 clinicians (58% of whom were obstetricians and the remainder midwives). The survey suggested that clinicians accept “maternal perception of decreased fetal movements” as a reliable indicator of fetal (in)activity with 74% of responders using this definition, in contrast to 2-65% for any numeric definition (25). The second survey (conducted by [name] in collaboration with applicants [name], [name] and [name] in Scotland in June 2012) was completed by two hundred clinicians, of whom 68% were midwives and the remainder obstetricians. In this second survey, 80% of clinicians accepted “maternal perception of decreased fetal movements” as a reliable indicator of fetal activity, reflecting concordance with the RCOG guideline. However only 80% advised women to attend when there was a reduction in perception of fetal movement, with less than 10% providing written information about this to women.

Regarding investigation and management of women presenting with decreased fetal movements, our first survey showed wide variation in clinical practice, with the majority (90%), but not all clinicians performing a CTG and with only 20% routinely requesting an ultrasound scan to assess fetal growth and liquor volume (25). Our second survey identified that, despite the introduction of RCOG guidelines in 2011, only 68% of responders had a policy to investigate women who report reduced fetal movements. Only a very small minority (less than 5%) would *routinely* request ultrasound in women presenting with reduced fetal movements, with the majority reserving ultrasound for women with further additional risk factors. The second survey also showed that access to ultrasound for women with decreased fetal movement with or without risk factors was suboptimal, with only 52% able to access within a 24hr period. Enthusiasm for induction of labour at term for women with more than one episode of decreased fetal movements was low, with nearly 25% of respondents suggesting that they would *never* offer induction of labour before 41 weeks in this scenario.

Taken together, the data from these two surveys suggest that that a trial based on increasing maternal awareness of decreased fetal movement would be acceptable to clinicians. Importantly, by standardizing management, greater access to scanning would occur, allowing identification of a greater number of women with FGR. Additionally, standardization of management around early delivery for those with identified fetal compromise or those at additional risk should improve outcomes.

1.2 RATIONALE FOR STUDY

The aim of this study is to test the hypothesis that a package of interventions consisting of strategies for increasing pregnant women's awareness of the need to report early when they perceive a reduction in fetal movements, followed with a management plan for identification and delivery of the "at risk" fetus in such women, will reduce rates of stillbirth.

2 STUDY OBJECTIVES

2.1 OBJECTIVES

2.1.1 Primary Objective

The primary objective is to answer the research question: Q1. Does the introduction of a protocol for detection and management of decreased fetal movements reduce rates of stillbirth?

2.1.2 Secondary Objectives

The secondary objectives are to answer the research questions:

Q2. What is the effect of the above intervention on rates of caesarean section and induction of labour?

Q3. What is the effect of the above intervention on rates of admission to the neonatal intensive care unit?

Q4. What is the effect of the above intervention on the proportion of women with fetal growth restriction remaining undelivered by 40 weeks gestation?

Q5. What is the acceptability of such a package of care to pregnant women and their health care providers?

Q6. What other process outcomes are influenced by the intervention, such as health care provider/patient interactions?

2.2 ENDPOINTS

2.2.1 Primary Endpoint

The primary endpoint is stillbirth (antepartum and intrapartum). We will use the CEMACH definition of stillbirth which is "a baby delivered without signs of life after 23⁺⁶ weeks". Where gestation is uncertain we will include all babies with a birth weight of 500g or more.

2.2.2 Secondary Endpoints

Other measures of perinatal mortality including:

- Stillbirth at 28 weeks gestation and above (WHO definition of stillbirth)
- Stillbirth at 22 weeks gestation and above
- Stillbirth at 37 weeks gestation and above
- Stillbirths amongst normally formed infants of 22 weeks gestation and above, 24 weeks gestation and above, 28 weeks gestation and above and 37 weeks gestation and above
- Perinatal mortality (defined as stillbirth at 24 weeks gestation and above and deaths in the first seven days of life)
- Rates of caesarean section
- Rates of induction of labour (overall)
- Rates of elective delivery (induction of labour and caesarean section prior to the onset of labour) overall
- Rates of induction of labour at 39 weeks 0 days gestation or later
- Rates of elective delivery (induction of labour and caesarean section prior to the onset of labour) in women delivered at 39 weeks 0 days gestation or later
- Mean gestation at delivery for women having induction of labour

- Rates of admission to the neonatal unit (and their reasons)
- Rates of admission to the neonatal unit for more than 48 hours
- Rates of admission to the neonatal unit for term babies (those born at 37 weeks 0 days or greater)
- Proportion of women with fetal growth restriction (less than the 10th centile, customised for gender) remaining undelivered at or after 40 weeks gestation
- Rates of spontaneous vaginal delivery

Other secondary outcomes are the baby parameters:

- Gestation at delivery
- Proportion of babies born preterm (\leq 37 weeks and 0 days gestation)
- Sex baby
- Birthweight of baby
- Birthweight centile (according to the Intergrowth birthweight centile calculator at <https://intergrowth21.tghn.org>)
- Apgar score at 5 minutes
- Proportion of babies with 5 minute Apgar score $<$ 4
- Proportion of babies with 5 minute Apgar score $<$ 7
- Resuscitation required at birth

We will also collect the following data:

maternal age, maternity unit of delivery, birthweight, gestation of delivery, parity, gestation, sex, smoking (current and ever), maternal BMI, number of babies (one or more), ethnicity (to allow a customised birthweight centile to be generated), method of delivery, Scottish index of multiple deprivation (or other deprivation scores) (where available) other neonatal variables: Apgar score, resuscitation required at birth, encephalopathy etc.

Adjustment will be made for the following variables: (maternal age, maternity unit of delivery, parity, smoking status, maternal BMI, number of babies [one or more] and ethnicity)

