Assess for risk factors for stillbirth and FGR. Confirm fetal viability. Perform anomaly scan, if not already done. If high risk of FGR arrange serial growth USS as per local policy /RCOG guideline.

What would the impact of this be on the clinical service?

In addition to a reduction in stillbirth, Tveit (1) showed that a policy of encouraging women to attend quickly after perception of decreased fetal movements had no significant increase in the total proportion of women attending with 6.2% of women presenting with decreased FM in third trimester prior to intervention and 6.6% of women after the intervention

However, it had a significant decrease in the proportion of women who waited more than 48 h to come to hospital (49% vs 54%) significant reduction in admission for induction (4.9% vs 7%) significant decrease in the number of admissions (11% vs 14%) non significant increase in the proportion of women with no follow up (69% vs 63%) a significant increase in the proportion of consultations which had ultrasound (94% compared with 86%).

In two other studies looking at the number of people attending with recurrent decreased fetal movements after 37 weeks, the figures were 0.2 – 0.5% of the obstetric population (2) (3). Again, Tveit showed that his intervention did not increase the number of women presenting, so the figure of 0.2 – 0.5% of the obstetric population should be robust. Even assuming an increase in the proportion of women presenting (at worst a doubling), this would result in only a modest increase in the proportion of women undergoing induction of labour (at worst, 0.4 - 1% of the obstetric population). In practice, the majority may have abnormal growth monitoring, so may already be undergoing induction of labour. These data suggest that, with the exception of the need for ultrasound, these policies should not increase the need for service delivery. Regarding ultrasound, in the worst case scenario (assuming that no woman presenting with reduced FM currently has USS, but that all women will in the future, and assuming that 6-7% of all women will present at some point in the third trimester after the intervention, then a hospital with 7000 deliveries per year will do no more than 2 - 8 extra scans per week. For induction of labour, a hospital with 7000 women would have no more than 0.4 – 1.3 inductions per week.

References:

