## 5.2 Secondary:

The study secondary endpoints are:

- Stillbirth at 28 weeks gestation and above (World Health Organisation (WHO) definition of stillbirth: "a baby born with no signs of life at or after 28 weeks' gestation")
- Stillbirth at 22 weeks gestation and above: Delivery of dead fetus at or more than 22 weeks gestational age determined by weeks of pregnancy at delivery or gestational age at diagnosis of fetal death, if known; or birth weight of 500 grams or more, if fetal gestational age is not known.
- Stillbirth at 37 weeks gestation and above
- Stillbirth amongst normally formed infants of 22 weeks gestation and above, 24 weeks gestation and above, 28 weeks gestation and above and 37 weeks gestation and above (a normally formed infant is identified by the variable Fetal abnormality marker =No in the study dataset)
- Perinatal mortality (defined as stillbirth at 24 weeks gestation and above and deaths in the first seven days of life)
- Rates of caesarean section
- Rates of induction of labour (overall)
- Rates of elective delivery (induction of labour and caesarean section prior to the onset of labour) overall
- Rates of induction of labour at 39 weeks 0 days gestation or later
- Rates of elective delivery (induction of labour and caesarean section prior to the onset of labour) in women delivered at 39 weeks 0 days gestation or later
- Mean gestation at delivery for women having induction of labour
- Rates of admission to the neonatal unit (and their reasons)
- Rates of admission to the neonatal unit for more than 48 hours
- Rates of admission to the neonatal unit for term babies (those born at 37 weeks 0 days or greater)
- Birthweight centile (according to the Intergrowth birthweight centile calculator at <https://intergrowth21.tghn.org>)
- Proportion of babies with fetal growth restriction (defined as "being less than the 10th centile (customised for gender) and remaining undelivered at or after 40+0 weeks gestation)
- Rates of spontaneous vaginal delivery

Other secondary outcomes are the baby parameters:

- Gestation at delivery
- Proportion of babies born preterm ( $\leq 37$  weeks and 0 days gestation)
- Sex baby
- Birthweight of baby
- Birthweight centile (according to the Intergrowth birthweight centile calculator at <https://intergrowth21.tghn.org>)
- Apgar score at 5 minutes
- Proportion of babies with 5 minute Apgar score  $< 4$
- Proportion of babies with 5 minute Apgar score  $< 7$
- Resuscitation required at birth

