## **8 Population for Analysis**

### **8.1 Intent to treat population**

The intention-to-treat (ITT) population will include all babies of women delivering at one of the AFFIRM study maternity units for the duration of the study.

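### Overall induction, elective delivery and gestation at induction count inductions done after fetal death, so a fall in antepartum stillbirth can partly mask a small rise in inductions of live pregnancies

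*Protocol*

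**What the plan says.** Protocol 2.2.2 lists "Rates of induction of labour (overall") and "Mean gestation at delivery for women having induction of labour" as secondary endpoints. SAP 5.2 repeats them and also has "Rates of elective delivery (induction of labour and caesarean section prior to the onset of labour) overall". None of the three carries a condition on whether the baby was alive at the start of the induction or caesarean.

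The analysis sections add no such condition. The SAP 8.1 population "will include all babies of women delivering at one of the AFFIRM study maternity units for the duration of the study", so stillborn babies are in it. SAP 9.6 applies the primary-outcome model to the induction and elective-delivery rates (9.6.7, 9.6.8) without changing the population, and SAP 9.7.1 takes gestation over all induced women.

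On purpose, protocol 1.1 says the trial will test "whether it does any harm (e.g. by increasing rates of caesarean section or induction of labour"), and secondary question Q2 asks about the same rates. On the link with the main result, protocol 2.2.1 states: "The primary endpoint is stillbirth (antepartum and intrapartum").

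**The concern.** If labour is often induced after an antepartum death, one delivery can count both as a primary-outcome event and as an induction. The change in the all-women induction rate is then the sum of two parts:

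change in all inductions = change in inductions of live pregnancies - fall in inductions after fetal death

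The first part answers the question about added intervention. The second follows from the effect on stillbirth. If the package reduces antepartum stillbirth, the second part pulls the result towards no increase, so the error is in the reassuring direction for an outcome that the protocol names as a possible harm.

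The same events affect gestation at induction. If inductions after fetal death happen earlier in pregnancy than other inductions, having fewer of them raises the mean, against any shift to earlier induction of live pregnancies.

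**Working it through.** **Inputs from the documents**
- Stillbirth rate 0.438%, cluster coefficient of variation (CV) 0.333, reductions of 25% and 30%, 24 groups, three per step, four-month periods (protocol 8.1). Nine periods (protocol Table 1).
- 58,000 + 50,000 = 108,000 deliveries a year (protocol 8.1). Over 36 months that is 324,000, or 324,000 / (24 x 9) = 1,500 per group and period.
- Worst-case effect on induction: "at worst, 0.4 - 1% of the obstetric population" (Appendix 4).

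**Assumptions, not in the documents**
- 85-92% of stillbirths antepartum, and 70-90% of those induced.
- Induction rate 20-35%, with between-group CV 0.1-0.333.
- For gestation: induction rate 20-30%, mean 32-34 weeks for inductions after death and 39.6 for the rest, SD 1.8-2.2 weeks, between-group SD 0.1-0.2 weeks.

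**1. Reproduce the plan's power.** The Hussey-Hughes variance with I = 24 groups and T = 9 periods is

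Var = I s2 (s2 + T t2) / [(IU - W) s2 + (U^2 + ITU - TW - IV) t2]

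with s2 = 0.00438 x 0.99562 / 1,500 = 2.907e-6; t2 = (0.333 x 0.00438)^2 = 2.127e-6; U = 108, W = 1,836, V = 612. The brackets are 2,592 - 1,836 = 756 and 11,664 + 23,328 - 16,524 - 14,688 = 3,780. This gives SE = 0.0388 percentage points.
- 30% reduction: 0.1314 / 0.03877 - 1.96 = 1.43, power 92.4% (stated 92.4%).
- 25% reduction: 0.1095 / 0.03877 - 1.96 = 0.86, power 80.6% (stated 80.7%).

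Halving the first active period of each group for the washout, and solving by generalised least squares, gives 88.5% and 75.0% (stated 88.2% and 74.6%). The model is close enough to use for the other outcomes.

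**2. Inductions after fetal death**
- Low: 0.00438 x 0.85 x 0.70 = 2.6 per 1,000 deliveries.
- High: 0.00438 x 0.92 x 0.90 = 3.6 per 1,000.

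**3. Offset in the induction rate**
- Low: 0.261% x 0.25 = 0.065 points.
- High: 0.363% x 0.30 = 0.109 points.
- Ceiling, if every stillbirth were induced: 0.438% x 0.30 = 0.131 points.

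Against Appendix 4: 0.065 / 1.0 = 7% and 0.109 / 0.4 = 27%.

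**4. Compare with the precision for induction.** The washout model of step 1 gives:

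| Assumed induction rate | SE (points) | 95% CI half-width (points) |
|---|---|---|
| 20% | 0.26-0.27 | 0.52 |
| 30% | 0.30 | 0.59-0.60 |
| 35% | 0.32 | 0.62 |

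The offset is 0.065 / 0.62 = 10% to 0.109 / 0.52 = 21% of the half-width. A true 1-point rise would appear as 1 - 0.109 = 0.89 to 1 - 0.065 = 0.94. At a 30% induction rate, an offset of 0.109 lowers power for a 1-point rise from about 91% to 83%, and for a 0.5-point rise from about 38% to 25%. The ceiling offset alone is an odds ratio of about 0.992 to 0.994.

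**5. Mean gestation at induction.** Shift = fall in the post-death share of inductions x gap in mean gestation.
- Low: (0.00065 / 0.30) x (39.6 - 34) = 0.012 weeks.
- High: (0.00109 / 0.20) x (39.6 - 32) = 0.041 weeks, or 0.29 days.

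The model SE is 0.021-0.032 weeks. Matched on induction rate, the shift is about 0.5-1.6 SE. For comparison, suppose an extra fraction e of women is induced at 38 weeks. The mean falls by about e / (rate + e) x 1.6:

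| Induction rate | e = 0.4% | e = 1% | Largest upward shift |
|---|---|---|---|
| 20% | 0.031 | 0.076 | 0.041 |
| 30% | 0.021 | 0.052 | 0.028 |

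The upward shift exceeds the fall only when its largest value meets the 0.4% rise. It never does so against a 1% rise.

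**The case against.** The strongest reply is that this is a choice of estimand. Q2 asks about rates of induction, and the all-women rate is a legitimate intention-to-treat answer. A woman whose baby is saved by induction might have been induced after a death otherwise, so her total is unchanged. Counting only live-fetus inductions would score that success as an added induction. This stands, and it is why the planned outcomes should not be replaced. It does not remove the need to show the two parts separately, because the net rate cannot tell a reader whether live pregnancies had more intervention.

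A second reply is that the effect is small and can be bounded from planned output: stillbirth is reported by phase (SAP 9.5), and the absolute fall caps the offset. That is also right. But the cap is not the estimate, and the site-level plot of stillbirth against induction at 37 weeks or more (SAP 9.10) does not separate live from dead either.

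A reader might infer more than this, and the documents do not support it:
- *That any fall in stillbirth automatically lowers the induction rate.* The primary endpoint includes intrapartum deaths, which are not inductions for fetal death, and a death averted by inducing a live baby leaves the total unchanged.
- *That a real rise would be hidden.* The offset cannot exceed about 13 per 10,000 deliveries.
- *That the outcomes at 39 weeks or later (SAP 9.6.9, 9.6.10) are affected as much.* They lack the same condition, but the documents give no stillbirth rate at those gestations. If inductions after death average 32-34 weeks, few would reach 39.
- *That SAP 9.7.1 is there to detect earlier induction as a harm.* Neither document says so.

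**Conclusion.** The point holds as a modest bias in a known direction. As worded, overall induction, overall elective delivery and gestation at induction include inductions after fetal death, and a fall in antepartum stillbirth would partly mask a small rise in live pregnancies. The masking matters most for rises of the size that Appendix 4 anticipates. The lower end of that range, 0.4 points, is below the interval half-width with or without masking, so the trial is imprecise there in any case. For gestation at induction the artefact is under a third of a day. It would offset part of a shift to earlier induction, and all of it only in the extreme case.

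The sizes rest on assumed values for the antepartum share, the share induced, the induction rate, the gestations and the SDs. Only the 0.131-point ceiling comes from the protocol's own figures alone, and it holds at its 30% reduction. The absence of an alive-at-onset condition needs no assumption.

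**What to change.** Keep the all-women outcomes as specified. Add to SAP 9.6.7, 9.6.8 and 9.7.1 a prespecified supplementary analysis that counts induction and pre-labour caesarean only when the birth was not an antepartum stillbirth.
- For the two rates, change only the numerator and leave the denominator as it is, so that no new selection enters.
- Use one definition in all regions. Protocol 7 draws on several data systems, and the data list in 2.2.2 does not mention timing of death. If any source cannot separate antepartum from intrapartum death, use live-born only throughout.
- Report inductions ending in stillbirth as a separate descriptive row by phase.

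The cost is one derived flag, a few lines of SAP text and a little more analysis. If the live-born definition is used, the few inductions ending in intrapartum death are left out. The 9.7.1 version restricts to babies who survived to the start of induction (or to birth), which the package may change, so it should be read as supportive only.
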